2 INTRODUCTION

2.1 STUDY RATIONALE

Uncontrolled asthma is an appropriate target for shared decision-making (SDM) interventions that support disease self-management as it is associated with higher asthma burden and worse clinical outcomes. To date, the application of SDM and community-based interventions targeting underserved communities have failed to address these disparities. Therefore, we will use patient and caregiver input to develop **BREATHE-PEDS - Brief intervention to Evaluate Asthma Therapy in Pediatrics** – a 9-minute SDM intervention focused on reducing the impact of erroneous beliefs on asthma control - and established its efficacy in this health disparity population. Our intervention is unique in that is a one-time brief, tailored intervention integrated into office visits, using the patient's own provider as the interventionist (e.g. scalable). Our pilot trial demonstrated high fidelity to **BREATHE-PEDS** delivery and

improved asthma control and reduced symptoms among adults compared to a dose-matched attention control condition.

This study addresses the important problem of uncontrolled asthma among a group at high risk for asthma and its adverse effects – urban minority children. Stakeholder-informed pragmatic trials are essential but are lacking in asthma intervention research. Our proposal addresses these weaknesses in the prior research.

2.2 BACKGROUND

A.1. Asthma's Impact is Significant in Minorities and Early Adolescents. Asthma is the most common chronic illness affecting 6 million US children¹. Prevalence and rates of uncontrolled asthma are highest among Black and Hispanic youth¹⁻⁵. Early adolescents (ages 10-14) have high asthma prevalence relative to younger children and adults¹. Disability-adjusted life years (DALYs), a measure of asthma burden, peaks at ages 10-14⁶⁻⁸, making asthma the third leading cause of DALYs⁷ in this age group⁶.

A.2. Early Adolescents have Poor Asthma Self-Management. Our team, and others, have demonstrated that early adolescents have sub-optimal asthma self-management, including trigger management and using medication preventively and when symptomatic¹⁰⁻¹⁴. Their poor self-management occurs in the context of unique developmental transitions that add challenges to self-management, including vulnerability to stress¹³ and increased independence and autonomy^{10,29,67}, as well as opportunities to render them good self-managers due to the developmental gains they also make⁶⁸. Yet, few interventions specifically target this age group.

A.3. Caregiver Engagement is Critical to Self-Management but is Lacking. Despite the fact that a gradual transfer of responsibility to youth is recommended⁷¹, caregivers often prematurely expect their child to assume responsibility for their asthma self-management⁷², with some transferring care as early as age 10⁷³. Early adolescents often report having more responsibility for their asthma care than their caregivers^{10,13}, despite a desire to share responsibility⁷². Thus, caregiver engagement is critical for optimal asthma management during early adolescence^{10,24,25}. Therefore, interventions are needed to engage caregivers to support their child's transition to independent self-management. Intervening with early adolescent-caregiver dyads has the potential for a synergistic effect improving asthma control beyond what an intervention for either alone might have.

A.4. Federally-Qualified Health Centers (FQHCs) are Optimal Settings for Asthma Interventions. Most (80%) asthma care is delivered by primary care providers (PCPs)⁹, and uncontrolled asthma is more common in these settings compared to specialty care⁷⁴. FQHCs are unique primary care settings providing asthma care for a greater proportion of minority patients with uncontrolled asthma⁵⁴. There are unique challenges to achieving asthma control in FQHCs: their clients live in - or near - the US poverty level⁵⁴ and PCPs in FQHCs have limited time and resources⁷⁵ to evaluate asthma control and to identify suboptimal self-management. This speaks to the pressing need for novel brief interventions integrated into clinical care.

A.5. Tailored SDM Interventions Can Promote Asthma Self-Management. The study is guided by the evidence-based model, Shared Decision-Making (SDM)⁷⁶, which posits that the best treatment decisions are informed by *patients' preferences*, the best available *scientific evidence*, and *clinician expertise*. PCPs facilitate discussions of risks and merits associated with options in the context of patient's goals and preferences, and in a manner that activates patients to engage in self-management⁵¹. The goal of SDM is to reach mutually agreed upon higher quality decisions that align patient's self-management decisions with guideline-directed evidence-based care^{77,78}. We have shown that SDM improves asthma control in adults^{30,53}, and SDM has been used in other areas of pediatric health⁵⁵⁻⁶⁰. Yet, there has been limited application in asthma⁶¹. A Cochrane review has shown some benefits of SDM in pediatric asthma, although confidence in findings was rated low-to-moderate because of the lack of suitable controls and high risk of performance and detection bias⁶².

A.6. Brief Dyadic SDM Interventions Can be Effective and Scalable. Brief interventions are effective in changing adults' health behaviors⁷⁹⁻⁸⁴. Non-asthma caregiver-child dyadic interventions resulted in

children reporting less anxiety⁸⁵, less disordered eating⁸⁶ and safer driving⁸⁷. Although less is known about brief asthma interventions targeting caregiver-youth dyads, one dyadic intervention was shown to improve caregiver-youth shared asthma management⁸⁵. These data suggest that targeting caregiver-child dyads may amplify, not dilute, intervention effects. Brief interventions (<20 minutes) make up for their brevity by including tailored advice, motivational interviewing (MI)⁵² and a plan for follow-up. A directed, patient-centered strategy for eliciting behavior change, MI helps patients explore and resolve ambivalence about recommended health behaviors while not confronting or seeking to change the health beliefs that underlie these behaviors⁵². The synergistic effects of tailoring, SDM, and MI “power” brief interventions in a way that more time- and labor-intensive generic interventions cannot match⁷⁹⁻⁸¹. Since implementation of SDM interventions has been restricted, in part, by burdensome protocols requiring multiple sessions, lengthy engagement and/or time-intensive training for PCPs – protocols ill-suited for FQHCs – we propose to develop **BREATHE-PEDS**, a brief (one-time, 9-minute) SDM intervention that utilizes MI delivered to caregiver-early adolescent dyads by PCPs during office visits for uncontrolled asthma.

A.7. Impact. This study will increase potential access to an asthma intervention for racial/ethnic minority early adolescents, an especially vulnerable group for poor asthma control. The impact of utilizing a brief, one-time FQHC-based intervention and intervening with caregiver-early adolescent dyads could be dramatic.

A.8. Strengths and Weaknesses in the Rigor of Prior Research. The scientific premise for this proposal is strong. Despite high asthma prevalence and morbidity among early adolescents and their unique developmental needs, the field is limited by a lack of developmentally appropriate interventions for this at-risk group. More specifically, most (76%) pediatric SDM interventions exclude children in decision-making⁶⁰, even though expert recommendation is that children be involved in health decision-making commensurate with their developmental age and maturity^{69,88}. Brief tailored dyadic SDM interventions delivered by PCPs during office visits for asthma directed at fostering evidence-based guideline-directed asthma self-management behaviors (e.g., trigger management, symptom monitoring, medication adherence) has great potential to improve asthma control. Other major limitations of prior research that we improve on include: time-intensive interventions focused on a single aspect of asthma self-management (i.e., medication adherence); intervention visits that occurred outside of clinical care; reliance on highly-trained interventionists; not tailoring interventions; failure to monitor intervention fidelity; lack of an attention control comparator; and a lack of formative process evaluations. We address these limitations and maximize the likelihood of sustaining our intervention and building capacity (scalability) by developing a brief (one-time 9-minute) tailored caregiver-early adolescent dyadic SDM intervention to effect early adolescent's asthma self-management behaviors, using PCPs as interventionists, and implementing rigorous fidelity monitoring protocols (see **C.2.a**) and an attention control group. Integrating self-management SDM discussions into clinical care offers several advantages, such as keeping PCPs more informed regarding their patients' status and health needs, offering them requisite knowledge to improve their asthma self-management. In addition, while prior pediatric SDM interventions often focused only on the caregiver^{60,89}, intervening simultaneously with caregivers can support the early adolescent's growing autonomy to self-manage asthma³⁷, and thus asthma control.

2.3 RISK/BENEFIT ASSESSMENT

2.3.1 KNOWN POTENTIAL RISKS

Asthma carries with it some inherent risk (morbidity and, rarely, mortality). Our intervention, however, is educational and behavioral and does not mandate (or prevent) changes in drug therapy or medical management by the study staff. All participants identified as having uncontrolled asthma on screening, regardless of whether they decide to enroll in the trial, will be scheduled for a visit with their PCP who will be notified at the time of screening that their patient's screening indicated uncontrolled asthma. Every attempt will be made to schedule the visit within 14 days of screening; patients will be instructed to seek immediate medical care if their condition deteriorates prior to that visit. While the behavioral

intervention itself is low risk, participants must have uncontrolled asthma to be eligible for enrollment. Because of this, we will ask the Safety Monitoring Board (SMC) to establish a threshold for asthma exacerbations and if we need stop rules, with the team's input.

Because the evaluation utilizes self-reported data, loss of confidentiality of study data is a potential risk. It is also possible that the participants will experience some inconvenience, embarrassment, distress, or fatigue while answering focus group questions/completing surveys. We will allow participants to skip questions and rest as needed.

2.3.2 KNOWN POTENTIAL BENEFITS

Complex behavioral interventions should be informed by stakeholders. Thus, focus group participants will contribute important data that will help us develop a tailored intervention.

The proposed research aims to help early adolescent patients with uncontrolled asthma improve their asthma control thus reducing asthma disparities. Given the minimal risks associated with our behavioral/educational intervention, we believe the benefits outweigh the risks, benefitting the participants. Specifically, those in the **BREATHE-PEDS** group will receive a one-time brief SDM intervention that is expected to improve communication about asthma control and erroneous beliefs, improving symptoms and SDM. Those in the control group may benefit from having a tailored discussion of healthy lifestyles.

We also believe this program will provide benefits to the FQHC personnel. Providers in both the active and control groups will have patients with uncontrolled asthma identified by research staff thereby giving them an enhanced understanding of uncontrolled asthma in their patient population. In addition, those in the **BREATHE-PEDS** arm may learn about erroneous beliefs that are barriers to asthma control and will learn how to deliver a brief behavioral intervention to enhance their patients' motivation to improve disease control.

2.3.3 ASSESSMENT OF POTENTIAL RISKS AND BENEFITS

Research staff will collect data at the designated time points and the PI will conduct the post-trial interviews. To minimize the risk of inconvenience, embarrassment, distress, or fatigue while completing surveys or interviews, we will allow participants to skip questions and rest as needed. Our team will be trained in all aspects of data collection, procedures for interviewing, and handling sensitive topics in data collection; they will also complete IRB training. Participants can discontinue participation at any time. Weekly team meetings will be used to discuss reactions to the surveys/interviews; we will provide re-training if needed.

3 OBJECTIVES AND ENDPOINTS

Objectives

We propose a feasibility trial to: 1) develop **BREATHE-PEDS** in a pediatric population (dyads of caregivers and their 10- to 14-year-old early adolescents with uncontrolled asthma) receiving asthma care in FQHCs; 2) evaluate the feasibility and acceptability of intervention procedures; and 3) assess intervention effects on asthma outcomes (monthly x 3 months post-intervention).

Endpoint

Primary Outcomes: asthma control as measured by improvements in Asthma Control Questionnaire (ACQ) score.

Secondary outcomes: (a) shared-decision-making as measured by scores the Shared Decision-making Questionnaire – 9 items, (b) Self-management as measured by the Medication Adherence Report Scale – Asthma (MARS-A), (c) asthma and ICS beliefs as measured by the Conventional and Alternative Management for Asthma, (d) asthma quality of life as measured by the Pediatric Asthma Quality of Life Questionnaire (PAQLQ) and Pediatric Asthma Caregiver's Quality of Life Questionnaire; and asthma exacerbations. We will also follow (l) Asthma Impairment and Risk Questionnaire (12 and older) and (m) and Asthma Responsibility Questionnaire scores over time.

Other measures: (1) demographics (age, sex); (2) health literacy as measured by the Newest Vital Sign and the Short Assessment of Health Literacy-English and Spanish.

4 STUDY DESIGN

4.1 OVERALL DESIGN

STUDY DESCRIPTION.

Our overall goal is to develop and test **BREATHE-PEDS (BRief intervention to Evaluate Asthma THErapy-Pediatrics)**, a shared decision-making intervention, among low-income urban minority adolescents with uncontrolled asthma.

AIMS. 1) develop **BREATHE-PEDS** in a pediatric population (dyads of caregivers and their 10- to 14-year-old early adolescents with uncontrolled asthma) receiving asthma care in FQHCs; 2) evaluate the feasibility and acceptability of intervention procedures; and 3) assess intervention effects on asthma outcomes (monthly x 3 months post-intervention).

HYPOTHESES.

1. The intervention will be feasible and acceptable as evidenced by: high rates of dyad recruitment and retention; PCP fidelity to the intervention protocol; and PCP and caregiver-child dyad satisfaction.
2. Over 3-months post-intervention, relative to controls, **BREATHE-PEDS** children will have improvement (a) in asthma control as measured by the *Asthma Control Questionnaire*⁶³⁻⁶⁵ (primary outcome), higher perceived SDM, and (b) on other asthma outcomes (secondary outcomes), including quality of life, school absences, lung functioning, and exacerbation.

STUDY PHASE. Phase 1 development and testing a behavioral intervention

STUDY DESIGN. This is a group-randomized clinical trial.

STUDY PROCEDURES.

Aim 1: Focus Groups.

Focus groups. Prior to recruiting for the trial, we will hold focus groups with caregivers (n =20); early adolescents (n =20) and dyads (n =10) (N=60), separately .

Aims 2 & 3: Group-randomized trial. This is a trial of a behavioral/educational intervention comparing the active condition **BREATHE-PEDS (BRief intervention to Evaluate Asthma THerapy-Peds)** to a dose-matched attention control condition (see below for detailed description of conditions). Active and control interventions are delivered once in 9-minutes by the participants' PCP during a single office visit. In each condition there are matched data collection points after baseline: 1-month 2-month, 3-month post-intervention. Considering the potential for visit disruptions due to Covid-19, we offer an alternative plan for the delivery of the intervention at a single telehealth visit (baseline) by phone or HIPAA-compliant videoconferencing platform.

Aim 2: Post-Trial Interviews. The PI will conduct post-trial semi-structured interviews with a purposive sample of ~6 participating clinicians, ~10 patient participants, and ~10 caregivers to ascertain their satisfaction with, and acceptability of, the active and control interventions. As part of our implementation evaluation, attempts will also be made to interview patient participants and PCPs who withdraw from the study (or PCPs who decline to enroll, if we have any), to better understand what it was that prevented their continued participation.

RANDOMIZATION.

We will randomly assign all eligible clinicians equally into the **BREATHE-PEDS** and the dose-matched attention control condition stratified for provider type (physician vs. nurse practitioner [NP]/physician assistant [PA]) using a computer-generated randomization list in advance of the trial. The first four physicians and first four NPs/PAs in each condition (**BREATHE-PEDS** and control) will then be invited to enroll (N=8). Those not selected (i.e., those remaining on the list) will be placed on "standby" if a replacement is needed. Invited PCPs signing consent will then be trained on the condition to which they were randomized. Each PCP will then enroll ~10 dyads meeting inclusion/exclusion criteria (N =85).

STATISTICAL ANALYSES.

Development and Intervention Feasibility. We will document recruitment, randomization and retention success, as well as process and implementation assessments.

Intervention Effects. Intervention effects will be assessed using linear mixed models (LMM) and generalized linear mixed models (GLMM) for continuous and categorical outcomes, respectively¹³². All hypothesis tests will be two-sided at level $\alpha=0.05$. The key outcome will be ACQ⁶³⁻⁶⁵ score; secondary measures will be examined to inform the future RCT. Separate models will be fitted for different outcome measures. If y_{ijt} is the outcome for patient j of provider i at time t , without loss generality then the following LMM will be used: $y_{ijt}=\beta_0+\beta_1*Group+\beta_2*t+\beta_3*INT+\beta_4*X_{ij}+\mu_i+\mu_{ij}+\epsilon_{ijt}$, where group, t , and INT are design variables. Group is an indicator for intervention arm and INT is an indicator for pre- or post-intervention. X_{ij} is a vector of possible PCP- and patient-level covariates. The random term $\mu_i \sim N(0, \sigma_1^2)$ is a PCP-specific random effect and $\mu_{ij} \sim N(0, \sigma_2^2)$ is a patient-specific random effect; $\epsilon_{ijt} \sim N(0, \sigma_\epsilon^2)$ is the model random error. To examine the effect of intervention on the outcome, we will conduct hypothesis test of $H_0: \beta_3=0$. We will explore differential intervention effect by sex (early adolescent and/or caregiver) and conduct exploratory analyses to determine if seasonality or differences in disease severity¹⁰⁸ between groups provide alternative explanations for findings.

Power & Sample Size. With a sample size of 10 dyads/PCP and 4 PCPs in each intervention arm (total n=10*4*2=80), and 20% attrition, we calculated the power to test the effect of intervention on ACQ. Power calculations were based on: (1) 4 repeated observations over the 3-month follow-up with a correlation of $\rho=0.8$ between repeated measures; (2) intra-cluster correlation among PCPs=0.2 to

account for clustering of patients from the same PCP; and (3) LMMs to estimate pre- and post-intervention differences. We estimated an 80% power to detect a small effect size ($d=0.15$). For ACQ, this is equivalent to detect a post-intervention difference of 0.15 (assuming $SD=0.9$).

Qualitative Data. Two or three coders will independently perform conventional content analysis¹³³. To enhance rigor, we will use multiple data sources (credibility), rich contextual descriptions (transferability), codebook and saturation tables (dependability) and audit trail (confirmability)¹³⁴⁻¹³⁷. NVivo 12 will manage data.

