9.4 STATISTICAL ANALYSES

9.4.1 GENERAL APPROACH

Participants will be described with respect to baseline characteristics (e.g., means, standard deviations, ranges, etc.) Descriptive data analysis will precede formal hypothesis testing to understand the data distribution and to check for outliers to determine the need for transformations of variables or special analytic techniques. We will also examine the patterns of missing data paying special attention to the balance of missing data in the study arms; linear and generalized linear mixed models provide unbiased estimates for data with missing at random when likelihood of missing is not related to the missing data and can be fully accounted for by variables where there is complete information. Intention-to-treat analyses will be conducted which requires data to be analyzed as randomized, regardless of whether participants completed some or none of the intervention. Based on our feasibility trial and the high retention rate in our previous trials, we anticipate 90% will provide baseline, 1-, 2-, and 3-month data.

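### Covariates enter the outcome model only as time-constant main effects, so the stated adjustment does almost nothing to a pre/post contrast in ACQ

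*Combined protocol and SAP*

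**What the plan says.** Section 4.1 (Statistical Analyses, Intervention Effects) and Section 9.4.2 (Aim 3) print the same linear mixed model. Its terms are an arm indicator, time t, a pre/post indicator INT, a covariate term β4·X_ij, a PCP random intercept, a patient random intercept and residual error. The covariate term "is a vector of possible PCP- and patient-level covariates". It carries provider and patient subscripts but no time subscript, is not multiplied by anything else, and names no covariate.

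The tested coefficient is β3. The text defines the variable ("INT is an indicator for pre- or post-intervention") and then the test: "To examine the effect of intervention on the outcome, we will conduct hypothesis test of" β3 = 0. The equation contains no arm-by-INT product.

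Section 4.1, but not 9.4.2, adds that the team will "conduct exploratory analyses to determine if seasonality or differences in disease severity" between arms could account for the findings. No model is given for this.

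Some missing data are expected. The power paragraph of Section 4.1 allows for it ("and 20% attrition, we calculated the power to test the effect of intervention on ACQ"), and Section 9.4.1 is more optimistic: "we anticipate 90% will provide baseline, 1-, 2-, and 3-month data".

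**The concern.** With a baseline and three follow-ups, a pre/post coefficient is estimated from differences within each child. A covariate that is constant within a child contributes nothing to those differences. An analyst who follows the printed model could add age, health literacy or provider type, see the ACQ result stay put, and report it as robust to adjustment. The stability would be algebra, not evidence.

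Only eight PCPs are randomised, so the arms can differ noticeably by chance in the children they contain. Where such a characteristic predicts how much ACQ changes, the difference between arms in change carries that imbalance, and the plan's only printed adjustment would leave it there.

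**Working it through.** **Plan's own figure.** The plan gives no figure for covariate adjustment. The nearest is 80% power at d = 0.15. With normal-approximation formulas for one-group and two-arm contrasts, no variant at n = 80, or 64 after attrition, came within 2 percentage points of it. Nothing below depends on that figure.

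**Inputs from Sections 4.1 and 9.2.** 4 PCPs per arm, 10 dyads per PCP, 20% attrition (80 × 0.8 = 64 children, 32 per arm), SD 0.9, correlation 0.8 between repeated measures, PCP ICC 0.2, target 0.15 ACQ points. *Assumed:* covariate slopes of 0.1 to 0.3 ACQ points of change per SD, and covariate ICCs of 0 to 0.2. The plan's ICC of 0.2 is for the outcome, not for any covariate.

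**Step 1, the algebra with complete data.** Split each variable into its child mean and the deviation from it.
- X_ij has zero deviation.
- INT has the same child mean (3/4) for everyone, which the intercept absorbs.
- Arm × INT has child mean 3/4 × arm, which the arm main effect absorbs.

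Both INT and arm × INT are therefore estimated from deviations alone, where X_ij is zero. Adding X_ij cannot move either estimate.

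**Step 2, simulation of the printed model.** 8 PCPs × 10 children × 4 occasions, REML, 60 trials per setting. Assumed: severity worth 0.6 ACQ points per SD in level, arms 0.5 SD apart. Effect of adding severity as a main effect:

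| Data | Term | Mean shift (points) | Mean shift (SE) | Largest shift |
|---|---|---|---|---|
| Complete | β3 as printed | 0.000 | 0 | 0.000 |
| Complete | INT read as arm × post | 0.000 | 0 | 0.000 |
| About 20% dropout | β3 as printed | 0.005–0.008 | 0.06–0.09 | 0.026 (0.31 SE) |
| About 20% dropout | INT read as arm × post | 0.009–0.015 | 0.09–0.15 | 0.051 (0.53 SE) |

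With complete data the SE was also unchanged to within 0.0001 (0.0815 against 0.0815 for β3). What moved was the arm main effect, for example from 0.283 to −0.027, and that is not the tested term.

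A second run used GLS with known variances, 64 children, 20% random dropout and a slope of 0.2. The arm × INT estimate had correlation 0.56 with the severity imbalance both before and after X_ij was added, and −0.07 once X × INT was added. The small movement under dropout is thus not useful adjustment.

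**Step 3, size of the imbalance.** For a covariate in SD units, the SD of the arm difference is √[2 × (ICC/4 + (1 − ICC)/32)].
- ICC 0: √(2/32) = 0.25
- ICC 0.05: 0.29
- ICC 0.1: 0.33
- ICC 0.2: √[2 × (0.05 + 0.025)] = 0.39

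Multiplied by the slope, the SD of the spurious arm difference in ACQ change is:

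| Slope | ICC 0 | ICC 0.2 |
|---|---|---|
| 0.1 | 0.025 | 0.039 |
| 0.2 | 0.050 | 0.077 |
| 0.3 | 0.075 | 0.116 |

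**Step 4, what X × INT buys.** Residual variance is 0.81 × (1 − 0.8) = 0.162. The variance of the arm difference in change (mean of three follow-ups minus baseline) is 0.162 × (1 + 1/3) × 2/32 = 0.0135, so the SD is 0.116. Adding the squared imbalance term at ICC 0.2 gives √(0.0135 + 0.0060) = 0.140 for slope 0.2 and √(0.0135 + 0.0135) = 0.164 for slope 0.3. Simulation agrees and shows the effect of X × INT on that SD:
- slope 0.2: 0.136 falls to 0.117
- slope 0.3: 0.175 falls to 0.121
- slope 0: 0.116 becomes 0.118

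**Step 5, X × INT without an arm × INT term.** With centred X and complete data, β3 is again unchanged. With uncentred X, β3 becomes the pre/post change at X = 0. For X centred on 5 and slope 0.2, it shifts by about −0.2 × 5 = −1.0.

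**The case against.** Several stronger readings are tempting, and the documents do not support them.

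- *Adjustment can never change the ACQ result.* This is exact only for a linear model with complete data. Losses are planned for, and single simulated trials moved by up to 0.53 SE, enough to shift a borderline p-value. For dichotomised outcomes such as MARS-A, analysed by GLMM, the cancellation is not exact even with complete data. In 60 simulated trials with assumed parameters the shift averaged 0.04 SE and reached 0.20 SE.
- *The severity check is bound to give false reassurance.* Section 4.1 does not say that severity goes in through X_ij. The same sentence plans a differential effect by sex, which needs an interaction absent from the printed equation, so that equation is not the full list of models. Stratification or a severity-by-time term would fit the text. Only the conditional statement stands: run as a main effect, the check is uninformative.
- *The planned primary comparison between arms is confounded.* As printed, β3 is a pre/post coefficient pooled over arms, not an arm comparison. The harm in Steps 3 and 4 arises once the test is rewritten as arm × INT.
- *The model ignores baseline differences.* It does not. The cancellation occurs because the pre/post contrast already removes constant differences in ACQ level. What is left is imbalance in predictors of change, and the documents give no figure for any such predictor.

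It is also fair that this is a feasibility pilot, and that the more basic defect is the choice of β3 itself. Even so, adding arm × INT alone would leave the covariate term just as inert.

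**Conclusion.** The point holds in a limited form. For ACQ and other continuous outcomes with a baseline, the printed covariate term has no effect on a pre/post contrast with complete data and very little under the planned attrition. It therefore does almost nothing about imbalance in factors that predict change.

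The cancellation is exact and assumption-free for complete data. The practical size is not: a spurious arm difference with SD from 0.025 to 0.116 points, against a 0.15-point target, rests on assumed slopes of 0.1 to 0.3 and assumed covariate ICCs of 0 to 0.2. If no covariate predicts change, nothing is lost by the present form. The improvement is worth making because it costs little and the equation needs rewriting anyway.

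**What to change.** In Sections 4.1 and 9.4.2, make two changes together:

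1. State the tested term as the between-arm contrast, arm × INT.
2. Name two or three baseline covariates that the trial already collects, for example provider type (the randomisation stratum) and age. Mean-centre each one and enter it as X_ij plus X_ij × INT. Main effects alone suffice for outcomes measured only after the visit.

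Run the exploratory severity check with the same interaction and name its measure. The reference attached to that sentence concerns a composite severity index, but no such index is listed among the endpoints in Section 1.1 or in the Section 8 table. The check should use something the trial actually records.

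The cost is a change of wording, one or two degrees of freedom per covariate, and a negligible loss of precision if a covariate does not predict change (SD 0.118 against 0.116). With eight PCPs the set should stay small and be fixed before unblinding. No new data are needed for the covariates. A severity check may need some if no suitable measure is collected.
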